8.2 SAFETY ASSESSMENTS

Assessment of Adverse and Serious Adverse Events:

AEs and SAEs will be monitored by study staff throughout the study. Staff will immediately notify the PIs and utilize the eCRF to record any AEs or SAEs. The PIs will review and categorize all AEs or SAEs and report them accordingly, as discussed below.

8.3 ADVERSE EVENTS AND SERIOUS ADVERSE EVENTS

8.3.1 DEFINITION OF ADVERSE EVENTS

This protocol uses the definition of AE from 21 CFR 312.32 (a): any untoward medical occurrence associated with the use of an intervention in humans, whether or not considered intervention-related.

8.3.2 DEFINITION OF SERIOUS ADVERSE EVENTS

This protocol uses the definition of SAE from 21 CFR 312.32 (a): An AE or suspected adverse reaction is considered "serious" if, in the view of either the investigator or study clinician, it results in any of the following outcomes: Death, a life-threatening AE, inpatient hospitalization or prolongation of existing hospitalization, a persistent or significant incapacity or substantial disruption of the ability to conduct normal life functions, or a congenital anomaly/birth defect. Important medical events that may not result in death, be life-threatening, or require hospitalization may be considered serious when, based upon appropriate medical judgment, they may jeopardize the patient or subject and may require medical or surgical intervention to prevent one of the outcomes listed in this definition.

8.3.3 CLASSIFICATION OF AN ADVERSE EVENT

8.3.3.1 SEVERITY OF EVENT

For AEs not included in the protocol defined grading system, the following guidelines will be used to describe severity.

1. **Mild** – Events require minimal or no treatment and do not interfere with the participant's daily activities.
2. **Moderate** – Events result in a low level of inconvenience or concern with the therapeutic measures. Moderate events may cause some interference with functioning.
3. **Severe** – Events interrupt a participant's usual daily activity and may require systemic drug therapy or other treatment. Severe events are usually potentially life-threatening or incapacitating. Of note, the term "severe" does not necessarily equate to "serious".

8.3.3.2 RELATIONSHIP TO STUDY INTERVENTION/EXPERIMENTAL MANIPULATION

All AEs will have their relationship to study procedures, including the intervention, assessed by an appropriately-trained clinician based on temporal relationship and his/her clinical judgment. The degree of certainty about causality will be graded using the categories below.

- **Definitely Related** – There is clear evidence to suggest a causal relationship, and other possible contributing factors can be ruled out. The clinical event, including an abnormal laboratory test result, occurs in a plausible time relationship to study procedures administration and cannot be explained by concurrent disease or other drugs or chemicals. The response to withdrawal of the study procedures should be clinically plausible. The event must be pharmacologically or phenomenologically definitive.

- **Probably Related** – There is evidence to suggest a causal relationship, and the influence of other factors is unlikely. The clinical event, including an abnormal laboratory test result, occurs within a reasonable time after administration of the study procedures, is unlikely to be attributed to concurrent disease or other drugs or chemicals, and follows a clinically reasonable response on withdrawal.
- **Potentially Related** – There is some evidence to suggest a causal relationship (e.g., the event occurred within a reasonable time after administration of study procedures). However, other factors may have contributed to the event (e.g., the participant's clinical condition, other concomitant events). Although an AE may rate only as "possibly related" soon after discovery, it can be flagged as requiring more information and later be upgraded to "probably related" or "definitely related", as appropriate.
- **Unlikely to be related** – A clinical event, including an abnormal laboratory test result, whose temporal relationship to study procedures administration makes a causal relationship improbable (e.g., the event did not occur within a reasonable time after administration of the study procedures) and in which other drugs or chemicals or underlying disease provides plausible explanations (e.g., the participant's clinical condition, other concomitant treatments).
- **Not Related** – The AE is completely independent of study procedures administration, and/or evidence exists that the event is definitely related to another etiology. There must be an alternative, definitive etiology documented by the clinician.

8.3.3.3 EXPECTEDNESS

The physician PI will be responsible for determining whether an AE is expected or unexpected. An AE will be considered unexpected if the nature, severity, or frequency of the event is not consistent with the risk information previously described for the study procedures.

8.3.4 TIME PERIOD AND FREQUENCY FOR EVENT ASSESSMENT AND FOLLOW-UP

The occurrence of an AE or SAE may come to the attention of study personnel during study visits and interviews of a study participant.

All AEs, not otherwise precluded per the protocol, will be captured on the appropriate eCRF. Information to be collected includes event description, time of onset, clinician's assessment of severity, relationship to study procedures (assessed only by those with the training and authority to make a diagnosis), and time of resolution/stabilization of the event. All AEs occurring while on study will be documented appropriately regardless of relationship. All AEs will be followed to adequate resolution.

Any medical or psychiatric condition that is present at the time that the participant is screened will be considered as baseline and not reported as an AE. However, if the study participant's condition deteriorates at any time during the study, it will be recorded as an AE.

Changes in the severity of an AE will be documented to allow an assessment of the duration of the event at each level of severity to be performed. Documentation of onset and duration of each episode will be maintained for AEs characterized as intermittent.

Study staff will record AE/SAEs with start dates occurring any time after the first intervention treatment session until the last post-treatment visit for each group. All reported events will be monitored until the

last post-treatment visit for each group. Any reported event that is definitely or probably related to the intervention will be followed until resolution or stabilization.

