1.2 SCHEMA

1.3 SCHEDULE OF ACTIVITIES

	Pre-screening	Consent	Pre-treatment 1	Pre-treatment 2	Study Intervention	Post-treatment 1	Post-treatment 2	Early Withdrawal Visit
Group 1: Immediate Start	Visit 0	Visit 1	Visit 2	N/A	Visit 3-38	Visit 39	Visit 40	
Group 2: Delayed Start				Visit 3	Visit 4-39	Visit 40	Visit 41	
Review Eligibility	X							
Informed Consent		X						
Randomization		X						
Demographics		X						
Medications		X	X	X	X	X	X	X
Blood Draw- in person			X	X		X	X	X
Strength & Cardiovascular Testing- in person			X	X		X	X	X
SCI-QOL- e-mail survey			X	X		X	X	X
Adverse Events (AE) Reporting					X	X	X	X
Treatment Adherence					X			

VISIT SCHEUDULE DESCRIPTION

All in-person visits will take place at: **HealthPartners Neuroscience Center, [name].**

1. Pre-screening Phone/Video Call (Groups 1 & 2)

- Duration: Approximately 30 minutes
- Research staff will:
 - Provide potential participants information about the study and ask whether they are interested in participating.
 - Determine whether they meet the inclusion/exclusion criteria for the study.
 - Ask participants for permission to communicate through e-mail for the study and assist them in setting up an account if they do not have one (e.g. send them study documents, QOL survey).
 - Schedule Consent Visit if the person is eligible for the study and e-mail the person the Informed Consent, Health Insurance Portability and Accountability Act (HIPAA), and HealthPartners non-discrimination forms.

2. Consent Phone Call (Groups 1 & 2)

- Duration: Approximately 1 hour via phone
- Research staff will:
 - Review the Informed Consent and HIPAA documents with potential participants.
 - Answer any questions of potential participants and ensure they understand the expectations of the study.
 - Ask participants to electronically sign the Informed Consent and HIPAA documents via REDCap and provide them electronic copies for their records.
 - Complete the Demographics short form in the relevant electronic case report forms (eCRFs) in Research Electronic Data Capture (REDCap), a secure web-based system.
 - Randomize the participant and schedule the Pre-treatment visit(s).

3. Pre-treatment Visit 1 (Groups 1 & 2)

- Duration: Approximately 1 hour in person
- Research staff will:
 - Complete the Medication review in REDCap.
 - Have the laboratory staff obtain a blood sample from the patient.

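### Adverse event recording starts only after the first exercise session under one rule in section 8.3.4, while other text in 8.3.4 and section 8.2 covers the whole study, so pre-exercise events are only partly captured

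*Combined protocol and SAP*

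**What the plan says.** The narrow rule is in the last paragraph of section 8.3.4: "Study staff will record AE/SAEs with start dates occurring any time after the first intervention treatment session", with recording ending at the group's final post-treatment visit. The rule names SAEs as well as AEs. In the section 1.3 schedule, the row "Adverse Events (AE) Reporting" is marked for the intervention, both post-treatment visits and the Early Withdrawal Visit. It is blank at consent, Pre-treatment 1 and Pre-treatment 2.

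The wider wording is in the same section and the one before it. Section 8.3.4 says "All AEs occurring while on study will be documented appropriately regardless of relationship". It treats conditions present at screening as baseline, and adds that if a participant's "condition deteriorates at any time during the study, it will be recorded as an AE". Section 8.2 says "AEs and SAEs will be monitored by study staff throughout the study".

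Two passages lean towards the narrow reading. Section 8.3.4 opens its capture rule with a proviso: "All AEs, not otherwise precluded per the protocol, will be captured on the appropriate eCRF". Section 8.3.1 defines an AE as "any untoward medical occurrence associated with the use of an intervention in humans", whether or not it is thought to be caused by that intervention. One passage leans the other way by implication, in section 8.3.3.2: "All AEs will have their relationship to study procedures, including the intervention", are to be graded by a clinician.

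**The concern.** Consent, randomization, the baseline blood draw and the strength and cardiovascular tests all come before the first exercise session. Group 2 also waits 12 weeks and then has a second draw and a second set of tests. Section 2.2.1 itself lists pain, bruising, dizziness and local infection as risks of a blood draw. Staff following the dated rule and the schedule would leave such an event off the AE form; staff following the general sentences would record it.

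What is at stake is the completeness of the safety record. Section 10.1.6 provides for no data safety monitoring board and relies on a rolling AE report reviewed at team meetings. Under the dated rule that report would omit events from pre-treatment procedures and from Group 2's delay. There would also be no control-group AE description for the first 12 weeks, the period of the randomized comparison in section 9.4.2.

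**Working it through.** The plan states no figure on this point to reproduce. The check is a comparison of texts, with a little counting.

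**1. Can the sentences be read together?**
- The proviso in 8.3.4 could let the dated rule govern the general capture sentence, and the schedule fits that reading.
- It does not settle the deterioration sentence, which applies at any time in the study, or section 8.2.
- Baseline is set at screening, not at the first session. A condition that first appears between the two is therefore not baseline and, under the start-date rule, not an AE either. It has no category.
- Sections 8.3.3.2 and 8.3.3.3 judge relatedness and expectedness against study procedures, which include draws and tests done before exercise. A definition tied to exercise alone sits badly with this.

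The conflict therefore remains.

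**2. What precedes the window?** Inputs: 10 participants per group (section 4.1); 3 draws in Group 1 and 4 in Group 2 (section 6.1.2), of which 1 and 2 are pre-treatment (section 1.3).
- Pre-treatment draws: 10 × 1 + 10 × 2 = 30.
- Next planned contact is the first exercise session: Group 1 after Pre-treatment 1 (10) plus Group 2 after Pre-treatment 2 (10) = 20 of the 30.
- Next planned visit is Pre-treatment 2, after the delay: Group 2 after Pre-treatment 1 = 10 of the 30.

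At the first session staff complete AE and medication forms, so an event after one of those 20 draws could be noticed there. Its start date would still put it outside the rule.

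**3. Scheduled AE checks in the first 12 weeks.** Group 1: 36 sessions plus Post-treatment 1 = 37. Group 2: 0.

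**4. How much of the delay does the 7-day question cover?** Inputs: 7-day look-back at every pre- and post-treatment visit (section 8.1); 12-week delay (section 4.1).
- Delay: 12 × 7 = 84 days.
- Covered at Pre-treatment 2: at most 7/84 = 8.3%, leaving 84 − 7 = 77 days.

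This assumes that Pre-treatment 2 falls at the end of the delay; the text does not fix its date.

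**5. Is the planned comparison of those 7-day reports equal between arms?** Section 9.4.1 compares them over the data collection period. Group 1 has 3 question visits (3 × 7 = 21 recall days) and Group 2 has 4 (4 × 7 = 28). As written, the comparison gives Group 2 more opportunity to report.

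**The case against.** The best defence is that 8.3.4 is the section on time period, its only dated rule is the first-session rule, and the schedule that staff work from agrees with it. The proviso and the AE definition then confine the general wording to events after exercise has begun. This has some force, and nothing in the documents shows that staff have in fact recorded events differently. It does not dispose of the deterioration sentence, the screening baseline or section 8.2.

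The second defence is that other routes exist, and this largely stands as partial cover. There is the 7-day question (8.1), medication review at each visit (6.5), recorded reasons for not continuing (5.4, 7.2) and physician clearance before exercise (6.1.2). None of these provides AE grading, and the timing of clearance in Group 2 is not stated.

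A reader might infer more than the documents support:
- *That pre-exercise events go unseen.* They may be noticed by the routes above; the gap is in recording them as AEs.
- *That serious events before exercise would not be reported.* Sections 8.3.6 and 8.4.2 state no first-session limit, although the 8.3.4 rule names SAEs, so that too needs reconciling.
- *That early leavers carried unrecorded harms.* Section 10.4 shows that some participants withdrew before the intervention, and the Early Withdrawal Visit is only for those who had begun it. But randomization takes place at the consent call, before any draw or test. How many left, and whether they had any procedure, is not stated.

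**Conclusion.** The inconsistency is real and should be corrected. If the start-date rule is followed, events from pre-treatment draws and tests and events in Group 2's 12-week delay are not recorded as AEs, and in the first 12 weeks AEs are recorded in one arm only.

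The size is modest. The affected procedures are blood draws and short tests, and partial cover exists. Section 9.4.5 plans no formal safety analysis beyond classifying events, so the start rule biases no planned test; the effect is on the safety description only. The counts assume 10 per group and a delay and program that run to plan.

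**What to change.** Reconcile sections 1.3, 8.2, 8.3.4 and 8.3.6 to one stated start of AE/SAE recording. Narrowing 8.2 and the general sentences of 8.3.4 would remove the contradiction but leave these events uncollected. Starting at the first study procedure matches the wider wording, the risks named in 2.2.1 and the grading in 8.3.3.2. In that case:
- mark AE reporting in both pre-treatment columns of the schedule;
- at Pre-treatment 2, ask Group 2 about the whole delay;
- ask once when a participant leaves after a study procedure but before the first session;
- in 9.4.5, report AEs descriptively by arm and period, stating that ascertainment is unequal (up to 36 session checks in Group 1 against one 12-week recall in Group 2) and that participants already past these visits were assessed under the present rule;
- in 9.4.1, restrict the between-arm comparison of 7-day reports to matching visits: Pre-treatment 1 in both groups, then Post-treatment 1 in Group 1 against Pre-treatment 2 in Group 2.

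Cost: 10 × 1 + 10 × 2 = 30 extra completions of an existing form at 20 participants. With 25 split 13/12 or 12/13 and all attending, it is 13 × 1 + 12 × 2 = 37 or 12 × 1 + 13 × 2 = 38. All fall at visits already planned; the question to early leavers is extra. A single 12-week recall will miss minor events. The data will be mixed across protocol versions, since section 10.4 shows that blood was already being drawn by version 4.0 (August 2022).

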8.3.5 ADVERSE EVENT REPORTING

In consultation with the PIs, a trained member of the study team will be responsible for conducting an evaluation of an AE and shall report the results of such evaluation to the reviewing IRB either at the time of continuing review or within 10 working days of becoming aware of the event if the event is considered to be serious or meets the definition of an unanticipated problem involving risks to study subjects or others.

8.3.6 SERIOUS ADVERSE EVENT REPORTING

In consultation with the PI and the study clinician, a trained member of the study team will be responsible for conducting an evaluation of a SAE and shall report the results of such evaluation to the reviewing IRB as soon as possible, but in no event later than 10 working days after the investigator first learns of the event.

8.3.7 REPORTING EVENTS TO PARTICIPANTS

Following IRB review of any AEs or SAEs, the PI will follow the IRB's recommended actions. This may include, but is not limited to, modifying the informed consent document or process, re-consenting current participants, providing information to past or current participants (e.g. whenever the information may relate to the participant's willingness to continue participants), and modifications to the protocol/research plan.

8.3.8 EVENTS OF SPECIAL INTEREST

N/A

8.3.9 REPORTING OF PREGNANCY

Women who are currently pregnant or planning to become pregnant during the study are excluded from this study. This is because it would be considered a high-risk pregnancy. If any participant who is undergoing exercise expectedly or unexpectedly becomes pregnant while active in the trial, the participant will be withdrawn from the study by the PI. The participant will be asked to complete an early withdrawal phone call in 7-14 days from the date the intervention was discontinued for safety follow-up.

If any participant who has completed all exercise sessions expectedly or unexpectedly becomes pregnant, the participant may remain in the study until study completion.

8.4 UNANTICIPATED PROBLEMS

8.4.1 DEFINITION OF UNANTICIPATED PROBLEMS

This protocol uses the definition of Unanticipated Problems as defined by the Office for Human Research Protections (OHRP). OHRP considers unanticipated problems involving risks to participants or others to include, in general, any incident, experience, or outcome that meets all of the following criteria:

1. Unexpected in terms of nature, severity, or frequency given (a) the research procedures that are described in the protocol-related documents, such as the IRB-approved research protocol and informed consent document; and (b) the characteristics of the participant population being studied;
2. Related or possibly related to participation in the research (“possibly related” means there is a reasonable possibility that the incident, experience, or outcome may have been caused by the procedures involved in the research); and
3. Suggests that the research places participants or others at a greater risk of harm (including physical, psychological, economic, or social harm) than was previously known or recognized.

8.4.2 UNANTICIPATED PROBLEMS REPORTING

The PIs will report unanticipated problems (UPs) to the reviewing IRB. The UP report will include the following information:

- Protocol identifying information: protocol title and number, PI's name, and the IRB project number
- A detailed description of the event, incident, experience, or outcome
- An explanation of the basis for determining that the event, incident, experience, or outcome represents an UP
- A description of any changes to the protocol or other corrective actions that have been taken or are proposed in response to the UP

To satisfy the requirement for prompt reporting, UPs will be reported using the following timeline:

- UPs will be reported to the IRB as soon as possible, but no later than 10 working days after the investigator first learns of the event

8.4.3 REPORTING UNANTICIPATED PROBLEMS TO PARTICIPANTS

Following IRB review of any unanticipated problems, the PI will follow the IRB's recommended actions. This may include, but is not limited to, modifying the informed consent document or process, re-consenting current participants, providing information to past or current participants (e.g. whenever the information may relate to the participant's willingness to continue participants), and modifications to the protocol/research plan.

9 STATISTICAL CONSIDERATIONS

9.1 STATISTICAL HYPOTHESES

- **Primary:**
We hypothesize that exercise will reduce inflammatory biomarkers.

- **Secondary:**
We hypothesize that exercise will improve strength and cardiovascular health.
- **Tertiary:**
We hypothesize that exercise will improve QOL.

9.2 SAMPLE SIZE DETERMINATION

The primary analysis is an superiority test of means on data from a parallel-group design. Assuming a standard deviation of 2.0 units for CRP, 1.0 units for IL-6, and 0.5 units for TNF- α ,⁸ and a true difference between means of 0, 10 subjects in each study group achieves 80% power at a 5% significance level to detect a 1.3 SD difference in mean change in inflammatory biomarkers between groups (PASS 2019 software). No interim analysis is planned. The potential effect on our power if our estimates for the effect size are displayed on the table below.

Power for N = 20 (10/arm)		
$\alpha = 0.05$		
CRP ($\sigma=2.0$)		
Δ	δ/σ	Power
2.3	1.2	0.70
2.6	1.3	0.80
3.1	1.5	0.90
IL-6 ($\sigma = 1.0$)		
Δ	δ/σ	Power
1.2	1.2	0.70
1.3	1.3	0.80
1.5	1.5	0.90
TNF- α ($\sigma=0.5$)		
Δ	δ/σ	Power
0.6	1.2	0.70
0.7	1.3	0.80
0.8	1.5	0.90

Based on preliminary estimates, we do not anticipate difficulty recruiting 25 participants. Physical Medicine and Rehabilitation physicians see approximately 25 individuals with SCI per month at the Neuroscience Center. Therefore we will need a 10% enrollment rate to reach our recruitment goal in the allotted time frame.

9.3 POPULATIONS FOR ANALYSES

All analyses will be performed on an intention-to-treat basis. If poor attendance is observed and/or patients choose to withdraw early, we will perform a per-protocol analysis as a sensitivity analysis.

9.4 STATISTICAL ANALYSES

9.4.1 GENERAL APPROACH

Discrete variables will be summarized using frequencies and percentages, while continuous variables will be summarized by means and standard deviations. If the continuous variables are found to be skewed, we will instead report medians and interquartile ranges. Statistical significance will be determined using p-values less than 0.05 and 95% confidence intervals, unless otherwise indicated. All inferential tests will be two-sided. For descriptive statistics (means, SDs, proportions) where no inferential statistics were conducted, we will refrain from making confirmative statements. All covariates will be pre-specified in the sections below. Any additional analyses will be described as post-hoc and exploratory.

Distribution of the outcome variables will be assessed prior to conduct of our analyses to determine if the planned tests are appropriate and to identify outliers. If variables are found to be non-normally distributed and/or outliers are present we will explore the use of log-transformations or non-parametric tests such as the Kruskal-Wallis test.

Patients who do not complete all assessments required for a given analysis will be excluded from the model/test and described separately. If missingness > 10% within the full analytic dataset, a comparison of participants with and without missing values will be performed and used to inform possible next steps (imputation, feasibility assessment of program, etc.). Reports of injury, illness, and life events occurring during the data collection period will be summarized and compared between arms. These summaries will be used to inform possible sensitivity analysis as described in section 9.4.10. All analysis will be performed in SAS 9.4 using two-sided alphas of 0.05 to determine significance.

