7.2 PARTICIPANT DISCONTINUATION/WITHDRAWAL FROM THE STUDY

Participants are free to withdraw from participation in the study at any time upon request.

An investigator may discontinue a participant from the study for the following reasons:

1. Participant has not completed a intervention treatment session for > 10 days, unless a participant has an illness, such as COVID-19. In this case, additional time may be allowed, as determined by the investigator.
2. Significant study intervention non-compliance during exercise sessions
3. Lost-to-follow up; unable to contact subject (see **Section 7.3, Lost to Follow-Up**)
4. Any event or medical condition or situation occurs such that continued collection of follow-up study data would not be in the best interest of the participant or might require an additional treatment that would confound the interpretation of the study
5. The participant meets an exclusion criterion (either newly developed or not previously recognized) that precludes further study participation

The reason for participant discontinuation or withdrawal from the study will be recorded on the relevant eCRF. Subjects who sign the informed consent form and are randomized but do not receive the study intervention may be replaced. Subjects who sign the informed consent form, and are randomized and

receive the study intervention, and subsequently withdraw, or are discontinued from the study, will not be replaced.

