9.4.2 ANALYSIS OF THE PRIMARY ENDPOINT(S)

The primary outcome, change in inflammatory biomarker (CRP, IL-6, TNF- α), will be measured using a series of blood draws as described in **Section 6.1**. For our primary analysis, we are interested in the change over the course of the first 3 months, during which group 1 completes the exercise program and group 2 acts as a control. The change in inflammatory biomarker will be calculated by measuring the difference between the first and second measurement for each participant. We will then present the mean change by group with corresponding standard deviations. Analysis of covariance (ANCOVA) will be used to compare the change in each of the 3 inflammatory biomarkers between groups: An unadjusted model will account for a participant's baseline biomarker measurement while an adjusted model will include the set of covariates identified in **Section 9.4.6**. If these analyses identify a significant difference in change of inflammatory biomarkers associated with participation in the exercise program, next steps will assess if this change is still present three months after completing the exercise program. Using data from both groups in aggregate, paired t-tests will be used to compare the inflammatory marker level directly after participation in the exercise program and inflammatory marker levels three months afterward.

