9.4.10 EXPLORATORY ANALYSES

Exploratory outcomes (e.g. treatment adherence) will be compared between groups with Student's t-test, Chi-square test, and Mann-Whitney-U test and mixed-model ANOVAs, as appropriate.

Planned sensitivity analysis includes per-protocol analyses to accompany the main intent-to-treat results. Patients who choose to withdraw early and complete the early withdrawal assessment will be analyzed separately from those who complete the intervention as planned. If the results from the per-protocol analysis demonstrate inconsistent findings from the main intent-to-treat analysis, the interpretation of any observed intervention effects will be qualified in all future presentation of the results. If necessary, we will conduct a sensitivity analysis in which we exclude participants that had protocol deviations (e.g. large delays between treatments) and those that report any injury, illness, or life events during the data collection period.

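### The primary analysis labelled intention-to-treat is by default complete-case: people withdrawn before week 12 are not asked for the week-12 draw, and the status of replaced participants and exit blood is not settled

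*Combined protocol and SAP*

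**What the plan says.** Section 9.3: "All analyses will be performed on an intention-to-treat basis". The set is not defined further. Section 9.4.10 repeats the label: "Planned sensitivity analysis includes per-protocol analyses to accompany the main intent-to-treat results".

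Section 9.4.1: "Patients who do not complete all assessments required for a given analysis will be excluded from the model/test and described separately". It adds: "If missingness > 10% within the full analytic dataset, a comparison of participants with and without missing values will be performed". Imputation is named there only as one possible later step, with no method.

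Section 9.4.2 restricts the primary comparison to the first 3 months, with Group 2 as control. The outcome is "calculated by measuring the difference between the first and second measurement for each participant".

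On leaving and replacement:
- Section 7.1 withdraws people from the study and asks for one exit visit, with blood, within 14 days of stopping the intervention. Section 1.3 item 8 limits that visit to people who began the intervention. Section 8.3.9 gives a participant withdrawn for pregnancy a safety phone call.
- Section 7.2: "Subjects who sign the informed consent form and are randomized but do not receive the study intervention may be replaced". People who started and then left are not replaced. Amendment 5.0 (Section 10.4) raised enrolment to 25 for such replacements.
- Section 9.4.10, among the sensitivity analyses: "Patients who choose to withdraw early and complete the early withdrawal assessment will be analyzed separately from those who complete the intervention as planned".

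**The concern.** A result based only on people with both draws would be reported as intention-to-treat, although randomisation no longer guarantees that the remaining groups are comparable. With 10 per arm, two or three exclusions matter.

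Loss related to outcome is plausible on the protocol's own statements. Section 2.1 says that these markers are higher in people with medical complications, and Section 8.1 records illness because it may affect them. That illness makes people leave is an assumption; the documents give no reasons for leaving.

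The arms are also handled differently in the 12 weeks of the primary comparison. A Group 1 leaver who has started is not replaceable and is normally asked for an exit draw. A Group 2 leaver who is still waiting is replaceable and has no exit visit.

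**Working it through.** **1. The plan's own figure.** Section 9.2: 10 per arm, two-sided 0.05, 1.3 SD, 80% power. For a two-sample t-test, the noncentrality is d × √(n/2) = 1.3 × √5 = 2.91 on 18 df, giving power 0.785. At d = 1.325 (printed as 1.3) power is 0.800. The figure reproduces. It needs 20 evaluable people: at d = 1.325, power is 0.78 with 9 and 10 evaluable, and 0.69 with 8 and 8.

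**2. What the rules do to each kind of participant.**

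| Situation | Week-12 draw | Exit draw | Replaceable | Primary model |
|---|---|---|---|---|
| Either group, poor attendance, both draws given | taken | not applicable | no, once started | included |
| Group 1, stops after starting, before week 12 | not sought | asked for within 14 days (pregnancy: phone call) | no | excluded, unless exit blood counts as the second draw |
| Group 1, leaves before the first session | not sought | none | yes | excluded |
| Group 2, leaves during the delay | not sought | none | yes | excluded |
| Group 2, leaves after Pre-treatment Visit 2, before the first session | already taken | none | yes | has both draws; retention not stated |

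**3. Size under assumed losses.** Not from the documents: numbers lost, arm, selection strength and a baseline/12-week correlation of r = 0.5. The null is true; ANCOVA of change on baseline and arm; leavers are those ranked highest on a score correlated ρ with the change; 40,000 trials per cell. Entries are absolute bias in SD of change / two-sided type I error.

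| Loss | ρ = 0.3 | ρ = 0.5 | ρ = 1.0 (exactly the largest risers leave) |
|---|---|---|---|
| Group 1, 2 of 10, not replaced | 0.07 / 5.4% | 0.12 / 5.8% | 0.25 / 9.5% |
| Group 1, 3 of 10, not replaced | 0.10 / 5.5% | 0.18 / 6.8% | 0.36 / 13.5% |
| Group 2, 2 of 12, replaced | 0.06 / 5.4% | 0.10 / 5.9% | 0.22 / 9.5% |
| Group 2, 3 of 13, replaced | 0.09 / 5.6% | 0.14 / 6.5% | 0.29 / 12.7% |

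With loss unrelated to outcome, bias is 0 and type I error 4.9 to 5.2%. With r = 0.3 or 0.7, the ρ = 0.5 results range over 0.09 to 0.19 SD and 5.8 to 7.0%.

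A hand check for 2 of 10: the two largest of 10 standard normal values average 1.54 and 1.00, so the remaining eight average −2.54/8 = −0.32. At r = 0.5 the change correlates −0.5 with baseline, so adjustment leaves about 1 − 0.25 = 0.75 of this: 0.24 at ρ = 1.0 and 0.5 × 0.24 = 0.12 at ρ = 0.5. Both agree with the table.

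Against the 1.3 SD planning effect: 0.10/1.3 = 8% to 0.18/1.3 = 14% at ρ = 0.5, and 0.22/1.3 = 17% to 0.36/1.3 = 28% in the extreme case.

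**4. Direction.** Losing people with rising markers from Group 1 favours exercise. Losing them from Group 2 works against it: at ρ = 0.5, false findings of benefit fall to about 1.1 to 1.5%, below the nominal 2.5%.

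**5. What is not arm-difference bias.** Equal loss of 2 or 3 in both arms, with nobody replaced, gives bias 0.00 but type I error of about 8 to 9.5% at ρ = 1.0. If only Group 2 is then replaced, bias is 0.01 to 0.03 at ρ = 0.5 and 0.03 to 0.08 at ρ = 1.0, so replacement itself adds little.

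**6. The 10% trigger.** Taking everyone randomised as the denominator, it does not fire at 2/20 = 10.0% or 2/22 = 9.1%. It fires at 3/20 = 15.0% or 3/23 = 13.0%.

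**7. What helps.** Multiple imputation from baseline and arm leaves the Group 1 bias at 0.12 and 0.18 (ρ = 0.5; 2 and 3 lost). Obtaining the draws does help: with 3 of 13 lost from Group 2 and ρ = 1.0, recovering 0, 1, 2 or 3 at random gives bias 0.29, 0.17, 0.08 and 0.00.

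**The case against.** The strongest reply is that the plan does fix a method (exclusion, with those excluded described separately) and that it has safeguards: rescheduling (7.3), extra time for illness (7.2), COVID-19 postponement (10.2), comparison of illness reports between arms (9.4.1), and per-protocol and illness-exclusion sensitivity analyses (9.4.10). With one follow-up value and baseline in the model, complete-case ANCOVA is valid if loss depends only on baseline and arm. Every loss figure above is assumed, and the effect is modest outside the extreme case.

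Most of this stands. It means that a different primary missing-data method is not required, particularly as imputation from baseline and arm left the bias unchanged. But no safeguard obtains week-12 blood from someone already withdrawn, defines the primary set, or makes the label right.

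Stronger readings that a reader might infer, and that the documents do not support:
- That everyone who leaves lacks the primary outcome. A Group 2 participant who leaves after Pre-treatment Visit 2 already has the second draw.
- That the plan is silent on exit blood. Section 9.4.10 separates voluntary early withdrawers with an exit assessment. The gap is narrower: the rule sits under sensitivity analyses, does not cover investigator withdrawals, and is not reconciled with 9.4.2.
- That Sections 7.1 and 1.3 flatly conflict on who has an exit visit. Section 7.1 is about stopping the intervention and times the visit from that date, so its natural reading is people who started.

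**Conclusion.** The point holds on the text. As written, a complete-case result would be presented as the main intention-to-treat result, and nothing says whether replaced participants are in it. This should be fixed before analysis.

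The bias may be zero. Under one-arm loss of 2 or 3 people it is about 0.10 to 0.18 SD of change at selection correlation 0.5, with type I error about 6 to 7%, and 0.22 to 0.36 SD in the extreme case. These figures rest on assumed losses and r = 0.5.

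A reader might infer that the trial is biased towards exercise, or that replacement is the cause. Neither follows: the direction depends on which arm loses people, the documents give no losses by arm, and replacement contributes little. Nor should the extreme-case error rates be read wholly as arm-difference bias, because equal loss also raises them.

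**What to change.** 1. **Follow-up.** Seek the scheduled 12-week draw from every willing randomised participant in both arms, including those who stopped, did not start or were replaced, unless ground 4 of Section 7.2 applies. Reconcile this with the follow-up in Section 1.3 item 8, Section 7.1 and Section 8.3.9.
2. **Primary set.** Define it as all randomised participants analysed as randomised, including anyone replaced who has both draws. Randomisation precedes the first draw, so report by arm and timing those without a baseline or week-12 draw, and all replacements. State that earlier exit blood is not the second measurement, for both patient and investigator withdrawals.
3. **Label and sensitivity.** Call the result complete-case as randomised, not intention-to-treat. Pre-specify one sensitivity analysis that shifts missing changes separately by arm, over a range chosen by the sponsor.

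The cost is SAP wording, a short amendment and a few draws in the existing visit format, which participants may decline. Data from people who have already left cannot be recovered; for them, only the set definition, the label and the reporting can change.
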